9.3 POPULATIONS FOR ANALYSES

There will be one dataset for this pilot study of 10 patients.

9.4 STATISTICAL ANALYSES

9.4.1 GENERAL APPROACH

Peak VO₂ is measured as ml/kg/min or L/min and statistics will be presented as percent change between the peak VO₂ on voxelotor and baseline peak VO₂. As the primary objective of this study is to obtain clinical and laboratory information to justify a larger clinical efficacy trial of voxelotor in SCA patients, the results of this study will first be analyzed descriptively.

9.4.2 ANALYSIS OF THE PRIMARY EFFICACY ENDPOINT(S)

The primary endpoint is peak VO₂, which is a quantitative measurement from the CPET instrument. There will be a single measurement as a baseline and another single measurement after the study drug for each participant. Paired t-test will be used to compare the 2 peak VO₂s.

9.4.3 ANALYSIS OF THE SECONDARY ENDPOINT(S)

The secondary endpoint is a group of biochemical tests, each with a different scale and different unit of measure. For each biochemical test, there will be a baseline measurement and a measurement after the study drug for each participant. Appropriate statistical comparison will be used for each biochemical measurement.

9.4.4 SAFETY ANALYSES

AEs will be coded by MedDRA terminology. Each AE will be counted once for a given participant. Severity, relationship to study drug, expectedness, dates, outcome, and duration of AEs will be reported.

9.4.5 BASELINE DESCRIPTIVE STATISTICS

Not applicable. There will only be one group.

9.4.6 PLANNED INTERIM ANALYSES

Not applicable

9.4.7 SUB-GROUP ANALYSES

Not applicable

9.4.8 TABULATION OF INDIVIDUAL PARTICIPANT DATA

Individual participant data will be listed by measure and time point.

9.4.9 EXPLORATORY ANALYSES

There are no exploratory analyses.

10 SUPPORTING DOCUMENTATION AND OPERATIONAL CONSIDERATIONS

10.1 REGULATORY, ETHICAL, AND STUDY OVERSIGHT CONSIDERATIONS

10.1.1 INFORMED CONSENT PROCESS

10.1.1.1 CONSENT/ASSENT AND OTHER INFORMATIONAL DOCUMENTS PROVIDED TO PARTICIPANTS

Consent forms describing in detail the study intervention, study procedures, and risks are given to the participant and written documentation of informed consent is required prior to starting intervention/administering study intervention. The following consent materials are submitted with this protocol: sample consent and assent form, voxelotor information sheet.

10.1.1.2 CONSENT PROCEDURES AND DOCUMENTATION

Informed consent is a process that is initiated prior to the individual's agreeing to participate in the study and continues throughout the individual's study participation. Consent forms will be Institutional Review Board (IRB)-approved and the participant will be asked to read and review the document. The investigator will explain the research study to the participant and answer any questions that may arise. A verbal explanation will be provided in terms suited to the participant's comprehension of the purposes, procedures, and potential risks of the study and of their rights as research participants. Participants will have the opportunity to carefully review the written consent form and ask questions prior to signing. The participants should have the opportunity to discuss the study with their family or surrogates or think about it prior to agreeing to participate. The participant will sign the informed consent document prior to any procedures being done specifically for the study. Participants must be informed that participation is voluntary and that they may withdraw from the study at any time, without prejudice. A copy of the informed consent document will be given to the participants for their records. The informed consent process will be conducted and documented in the source document (including the date), and the form signed, before the participant undergoes any study-specific procedures. The rights and welfare of the participants will be protected by emphasizing to them that the quality of their medical care will not be adversely affected if they decline to participate in this study.

For subjects age < 18, the parent or legal guardian will sign the consent and the subject will sign the assent.

10.1.2 STUDY DISCONTINUATION AND CLOSURE

This study may be temporarily suspended or prematurely terminated if there is sufficient reasonable cause. Written notification, documenting the reason for study suspension or termination, will be provided by the suspending or terminating party to study participants, investigator, and GBT Medical Affairs Research Program and the IRB. If the study is prematurely terminated or suspended, the Principal Investigator (PI) will promptly inform study participants, the Institutional Review Board (IRB), and GBT Medical Affairs Research Program and will provide the reason(s) for the termination or suspension. Study participants will be contacted, as applicable, and be informed of changes to study visit schedule.

Circumstances that may warrant termination or suspension include, but are not limited to:

- Determination of unexpected, significant, or unacceptable risk to participants
- Demonstration of efficacy that would warrant stopping
- Insufficient compliance to protocol requirements
- Data that are not sufficiently complete and/or evaluable
- Determination that the primary endpoint has been met
- Determination of futility

Study may resume once concerns about safety, protocol compliance, and data quality are addressed, and satisfy the IRB and/or Food and Drug Administration (FDA).

10.1.3 CONFIDENTIALITY AND PRIVACY

Participant confidentiality and privacy is strictly held in trust by the participating investigators and the study team. This confidentiality covers the clinical information relating to participants. Therefore, the

study protocol, documentation, data, and all other information generated will be held in strict confidence. No information concerning the study or the data will be released to any unauthorized third party without prior written approval of the Principal Investigator.

All research activities will be conducted in as private a setting as possible.

The study monitor, other authorized representatives of the Principal Investigator, representatives of the Institutional Review Board (IRB), regulatory agencies or pharmaceutical company supplying study product may inspect all documents and records required to be maintained by the investigator, including but not limited to, medical records (office, clinic, or hospital) and pharmacy records for the participants in this study. The clinical study site will permit access to such records.

The study participant's contact information will be securely stored at each clinical site for internal use during the study. At the end of the study, all records will continue to be kept in a secure location for as long a period as dictated by the reviewing IRB, Institutional policies and requirements.

Study participant research data, which are for purposes of statistical analysis and scientific reporting, will be stored in a local secure database. This will not include the participant's contact or identifying information. Rather, individual participants and their research data will be identified by a unique study identification number. The study data entry and study management system used will be secured and password protected. At the end of the study, all study data will be de-identified and archived.

10.1.4 FUTURE USE OF STORED SPECIMENS AND DATA

Data collected for this study will be analyzed and stored in a password-protected file on the site server. After the study is completed, the de-identified, archived data will be held by the sponsor investigator. Permission for GBT to access data will be included in the informed consent.

No biological specimens will be retained and no genetic material will be collected in this study.

10.1.6 SAFETY OVERSIGHT

The study intervention is taking an oral, commercially available, FDA-approved drug and the study measurement is doing exercise studies, which is minimal risk. No DSMB is required.

10.1.7 CLINICAL MONITORING

This study is minimal risk, monitoring by PI and IRB is sufficient. No CMP is necessary.

10.1.8 QUALITY ASSURANCE AND QUALITY CONTROL

The clinical site will perform internal quality management of study conduct, data collection, documentation and completion. The PI will check the quality and accuracy of data entry. The exercise lab is a certified exercise lab and will conduct its own quality control. The research lab conducts quality control on all its instrumentation and lab protocols.

Summarized data will be provided to GBT in study progress reports.

10.1.9 DATA HANDLING AND RECORD KEEPING

10.1.9.1 DATA COLLECTION AND MANAGEMENT RESPONSIBILITIES

Data collection is the responsibility of the study team under the supervision of the principal investigator. The investigator is responsible for ensuring the accuracy, completeness, legibility, and timeliness of the data reported.

All source documents will be completed in a neat, legible manner to ensure accurate interpretation of data.

Hardcopies of the study visit worksheets will be provided for use when necessary as source document worksheets for recording data for each participant enrolled in the study. Data will be recorded in password-protected database accessible only by PI and the study personnel. Any source document on paper will be stored in locked cabinet in the Clinical Research Associate's office.

Clinical data (including adverse events (AEs), concomitant medications, and expected adverse reactions data) and clinical laboratory data will be entered a database designed for this study. The data system includes password protection. Clinical data will be entered directly from the source documents.

10.1.9.2 STUDY RECORDS RETENTION

Study documents will be retained for 3 years or as required by the IRB after completion of the study. No records will be destroyed without the written consent of the Sponsor-Investigator, if applicable. It is the responsibility of the investigator to determine when these documents no longer need to be retained.

10.1.10 PROTOCOL DEVIATIONS

Examples of protocol deviations in this study include:

- Noncompliance with voxelotor
- Starting the study drug before baseline CPET
- Failure to send study labs

Protocol deviations will be reported to the Sponsor-Investigator and a decision will be made whether to discontinue the subject from study, if the data from the subject will become uninterpretable.

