1.2 SCHEMA

1.3 SCHEDULE OF ACTIVITIES (SOA)

| Procedures | Screening/ Enrollment Day -60 | Study Visit 1 Day -30 +/- 7 days | Study Visit 2 Day - 29 to -1 | Study Visit 3 Day 1 +/- 14 days | Study Visit 4 Day 30 +/- 7 days | Study Visit 5 Day 60 +/- 7 days | Study Visit 6 Day 60-89 | Final Study Visit 7 Day 90 +/- 14 days |
|--|-------------------------------------|--|------------------------------------|---------------------------------------|---------------------------------------|---------------------------------------|----------------------------|---|
| Informed consent | x | | | | | | | |
| Demographics | x | | | | | | | |
| Medical history | x | | | | | | | |
| Dispense voxelotor ^d | | | | x | x | x ^d | | |
| Concomitant Medication review | x | x | | x | x | x | | x |
| Physical exam | x | x | | x | x | x | | x |
| Vital signs, Ht, Wt | x | x | x | x | x | x | x | x |
| Performance status | x | | | | | x | | x |
| Routine labs ^a | x | x | | x | x | x | | x |
| Study labs ^b | | x | | | | x | | |
| Pregnancy test ^c | x | | | x | x | x | | |
| Adverse event review and evaluation | x | | | x | x | x | | x |
| Schedule CPET | | x | | | | x | | |
| CPET | | | x | | | | x | |
| CGI, PGI assessments | | | | | | | | x |
| Data collection and entry | x | x | | x | x | x | | x |

^a Routine labs: CBC diff, retic, CMP, LDH, haptoglobin, Hemoglobin F or hemoglobin electrophoresis

^b Study labs: Send to UCSF [name] lab: % F cells, P50 oxygen dissociation, ektacytometry, point of sickling (POS), dense cells.

^c Pregnancy test: All menstruating female participants

^d Participants will be treated with voxelotor for at least 8 weeks before the 2nd CPET, which will be scheduled as close to the date following 8 weeks of treatment with voxelotor. Participants will continue voxelotor until the 2nd CPET is completed.

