4.4 END OF STUDY DEFINITION

A participant is considered to have completed the study if he or she has completed all phases of the study including 2 CPETs and the last visit shown in the Schedule of Activities (SoA), Section 1.3.

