6.2.1 ACQUISITION AND ACCOUNTABILITY

Voxelotor tablets will be supplied in high-density polyethylene bottles with induction-sealed polypropylene child-resistant caps. Packaged and labeled drug product (voxelotor) will be supplied by GBT and shipped to the clinical site. Study drug will be dispensed at Visit 3 in bottles of 90 tablets. The PSV pharmacist will receive the bottles, which will be stored in a temperature controlled locked med room. The PI will dispense the drug. The study coordinator or PI will pick up/sign pharmacy log and dispense study drug to participant with instructions during the study visit.

The participants will bring the medicine bottle back to clinic each month. Unused pills will be counted and recorded. Dates of receipt, dispense, return, lot numbers, and pill counts will all be recorded in a log.

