6.4 STUDY INTERVENTION COMPLIANCE

Each bottle of voxelotor contains 90 tablets. The dose is 3 tablets a day. Each bottle lasts 30 days. Participants will be scheduled for clinic visits no longer than 30 days apart. Participants will be given a bottle of voxelotor at a clinic visit and will be asked to bring back the bottle with left over pills in it. Compliance will be determined by pill counting. The number of pills remaining will be counted and subtracted from 90 to get the number of pills taken, which can be divided by 3 to get the number of days the drug was taken. The difference between the number of days drug was taken and the number of days between the clinic visits is the number of days drug was missed.

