7.2 PARTICIPANT DISCONTINUATION/WITHDRAWAL FROM THE STUDY

Participants are free to withdraw from participation in the study at any time upon request.

An investigator may discontinue or withdraw a participant from the study for the following reasons:

- Pregnancy
- Significant study intervention non-compliance
- If any clinical adverse event (AE), such as hypersensitivity to the study drug, laboratory abnormality, or other medical condition or situation occurs such that continued participation in the study would not be in the best interest of the participant
- If the participant meets an exclusion criterion (either newly developed or not previously recognized) that precludes further study participation
- Participant unable to perform CPET
- Participant unexpectedly moves to another location not within travel distance of the exercise lab and is unable to complete the 2nd CPET before moving

The reason for participant discontinuation or withdrawal from the study will be recorded on the Case Report Form (CRF). Subjects who sign the informed consent form and subsequently withdraw, or are withdrawn or discontinued from the study, will be replaced.

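### Sections 7.2 and 10.1.10 allow a participant who already has both CPETs to be removed and replaced, so the primary change in peak VO2 is not protected from result-dependent selection

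*Protocol*

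**What the plan says.** **Removal.** Section 10.1.10 gives three examples of deviations: "Noncompliance with voxelotor", starting drug before the baseline CPET, and study labs not sent. All deviations go to the Sponsor-Investigator. The rule that follows is: "a decision will be made whether to discontinue the subject from study, if the data from the subject will become uninterpretable". Section 7.2 separately lets an investigator withdraw a participant for "Significant study intervention non-compliance". Section 6.4 says "Compliance will be determined by pill counting" but sets no threshold.

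**Replacement.** Section 7.2 closes with: "Subjects who sign the informed consent form and subsequently withdraw, or are withdrawn or discontinued from the study, will be replaced".

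**Timing.** Footnote d of the Schedule of Activities (1.3) says: "Participants will continue voxelotor until the 2nd CPET is completed". Section 6.2.1 says: "The participants will bring the medicine bottle back to clinic each month. Unused pills will be counted and recorded". Under 4.4 a participant has finished only if he or she "has completed all phases of the study including 2 CPETs and the last visit shown in the Schedule of Activities"; that last visit is Visit 7.

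**Analysis.** Section 9.3 provides a single dataset for the 10 patients. Sections 9.1 and 9.4.2 specify a paired t-test on one baseline and one on-drug peak VO2 per participant.

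**The concern.** The study is open-label and single-arm (4.1). The Statement of Compliance makes the PI the Sponsor-Investigator, and under 10.1.9.1 the PI has access to the study database. The person to whom deviations are reported can therefore see the second CPET before a participant is discontinued, and the stated hypothesis is improvement. A participant whose peak VO2 did not rise is the one whose compliance is most likely to be questioned. If such a participant is replaced and only 10 patients are analysed, the mean change moves upward.

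Section 9.2 says the pilot exists to define the size of the change, and 9.4.1 says its results are meant to justify a larger trial. The main harm is thus an inflated estimate carried forward. The p-value is a lesser matter, because 9.4.1 puts descriptive analysis first.

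**Working it through.** **Step 1. Is there a period in which the result is known and the participant can still be removed?** From the Schedule of Activities:

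| Event | Nominal timing | Bearing on the point |
|---|---|---|
| Visit 3, first bottle | Day 1 ± 14 | count due at Visit 4 |
| Visit 4, second bottle | Day 30 ± 7 | count due at Visit 5 |
| Visit 5, third bottle | Day 60 ± 7 | count normally due at Visit 7 |
| Visit 6, second CPET | Day 60-89 | schedule lists only vital signs and the CPET |
| Visit 7 | Day 90 ± 14 | needed for completion (4.4) |

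At nominal dates the first two bottles cover Day 1 to Day 60, about 59 days against the planned 56 (8 × 7). Those counts exist before the second CPET. The third bottle covers the interval from Visit 5 to the CPET, nominally 0 to 29 days, and is normally counted after the result exists. Footnote d aims for a CPET soon after 8 weeks, so the interval should usually be short. Whatever its length, a participant tested at Visit 6 has not completed until Visit 7. One who withdraws or is discontinued in between falls under the 7.2 replacement rule.

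**Step 2. Does anything close that period?** Neither 7.2 nor 10.1.10 sets a cut-off at the second CPET, asks for a decision without sight of it, or defines the degree of non-compliance or loss of interpretability that triggers removal. No section keeps a removed participant's CPET pair in the analysis. Replacement plus one dataset of 10 points to the replacement taking that place, although this is not stated.

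**Step 3. How large could the effect be?** The plan has no figure to reproduce: 9.2 sets 10 patients and disclaims power, and no alpha or SD is given. Assumptions: within-person changes D are normal with true mean 0 and SD 1; n = 10; t = mean/(s/√10); two-sided 5% test, so the benefit tail is P(t > t(0.975, 9 df)), nominally 2.5%. Results are from 400,000 simulated trials, except the last row (200,000).

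| Removal rule | Bias of mean (SD of change) | Benefit tail |
|---|---|---|
| None | 0.00 | 2.5% |
| 10-50% deviate, all replaced whatever the result | 0.00 | 2.5% |
| 10% deviate, replaced only if D < 0 | +0.04 | 3.4% |
| 20% deviate, replaced only if D < 0 | +0.08 | 4.6% |
| 30% deviate, replaced only if D < 0 | +0.12 | 5.9% |
| Lowest of 10 always replaced | +0.155 | 8.2% |
| Lowest of 11 always dropped | +0.159 | 8.7% |

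**Check by hand.** With deviation rate p unrelated to outcome, bias = p × P(D < 0) × E(−D given D < 0) = p × 0.5 × 0.798 = 0.399p. This gives 0.040, 0.080 and 0.120 for p = 0.1, 0.2 and 0.3, as simulated. The mean number removed is 10 × p × 0.5 = 0.5, 1.0 and 1.5 participants.

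**Step 4. In percent change.** The protocol gives no SD. If the SD of within-person percent change is 8-12% (assumption), the 10-30% cases run from 0.04 × 8 = 0.3 to 0.12 × 12 = 1.4 percentage points. The lowest-of-11 case runs from 0.159 × 8 = 1.3 to 0.159 × 12 = 1.9 points. Section 2.2 cites a difference of about 10% with transfusion.

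**The case against.** The strongest reply is that the permission comes from silence. A reader might infer that the protocol authorises discarding a participant's CPETs once the result is seen. It does not say so: 10.1.10 speaks of leaving the study, its wording on interpretability looks forward, and replacing someone does not in itself delete that person's data. Section 8.4.1 speaks of keeping the number of evaluable subjects at 10, and a participant with both CPETs would naturally count as evaluable. An analysis plan could also define the analysis set. This stands as a limit on the claim. It does not remove it, because the discontinuation and replacement rules are fixed in this protocol and 7.2 makes no exception for a completed pair.

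A reader might also infer that compliance is generally unknown until after the outcome. Step 1 shows otherwise: only the Visit 5 bottle is late. Nor does the text support the idea that unsent labs alone remove a participant. Study labs are drawn at Visits 1 and 5, before the second CPET, and 10.1.10 acts only if the data become uninterpretable.

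Some protection exists. Section 7.1 allows drug to be resumed before the second CPET, 7.2 records reasons for withdrawal on the CRF, and 9.4.8 lists individual data. These help a reader detect selection but do not prevent it.

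Finally, the figures of 8-9% assume that the worst responder is always the one lost. That is an upper illustration for a single removal, not an expectation.

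**Conclusion.** The concern holds in a limited form. As written, a participant whose CPET pair is known can be removed on undefined grounds and must then be replaced, and nothing secures that pair's place in the primary analysis. The documents do not show that selection is intended, or that removed data are discarded.

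If removal depends on the result, the bias favours voxelotor: +0.04 to +0.12 SD at deviation rates of 10-30%, and about +0.16 SD in the single-removal worst case. If removal ignores the result, there is no bias and two-sided error stays at 5%. These sizes rest on normal changes, no true effect, an assumed two-sided 5% test and assumed deviation rates. The direction follows from removing low values and does not depend on the assumed SD or alpha. The effect is modest, but it falls on the one quantity the pilot is meant to estimate and is cheap to prevent.

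**What to change.** Amend 7.2, 9.3 and 10.1.10 to the following effect:

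- Every participant with a baseline CPET done before drug and a second CPET done after starting drug is included in the primary analysis and is not replaced, whatever the later pill count, missing study labs or withdrawal before Visit 7.
- Replacement applies only to participants without a second CPET.
- Deviations found after the second CPET are recorded with reason and date. They are handled only in a secondary analysis that leaves those participants out, shown beside the primary result.

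Withdrawal from treatment for safety is unaffected. The wording must be reconciled with 7.1, which sets a condition on drug-taking before the second CPET after an interruption. It must also be reconciled with 8.4.1, where replacing a participant who moves away is to be discussed with the sponsor, while 7.2 replaces automatically.

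The cost is a few sentences in an amendment, with no added visits or tests. The downside is that a poorly compliant participant stays in the primary mean and may dilute it slightly; the secondary analysis shows by how much.
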